# 9.5.8. Hypertriglyceridemia and Hypercholesterolemia

Hypertriglyceridemia:	Grade 3:	5.7-11.4 mmol/L (>500-<1,000 mg/dL)
	Grade 4:	>11.4 mmol/L (>1,000 mg/dL)
Hypercholesterolemia:	Grade 3:	≥7.77 mmol/L (>300 mg/L)
	Grade 4:	Not applicable

Toxicity management decisions should be based on fasted results. If elevated lipid levels are from a nonfasted blood draw, the draw must be repeated after an 8-hour fast.

Subjects who experienced asymptomatic triglyceride or cholesterol elevations of grade 3 or 4 may continue study medications unless clinical assessment foresees an immediate health risk to the subject.

Hypertriglyceridemia and hypercholesterolemia should be treated according to the specific guidelines for treating HIV-positive subjects (see Attachment 5). Current treatment guidelines specify different lipid thresholds for intervention for different degrees of cardiovascular risk. The presence or absence of other significant cardiovascular risk factors, which include smoking, age, family history of premature cardiovascular disease, diabetes, hypertension, low HDL cholesterol, and prior history of cardiovascular disease should be taken into account. Appropriate clinical management of hyperlipidemia in the setting of HIV disease should be started in a timely fashion if applicable.

# 9.5.9. Lipodystrophy/Fat Redistribution/Body Changes

Investigators are requested to avoid using the term 'lipodystrophy acquired' or 'fat redistribution' to describe and report body fat abnormalities, as these terms are not descriptive nor fully accurate. The different symptoms and gradings are listed in the DAIDS grading table (see Attachment 2) under Endocrine/Metabolic. The following terms are included: lipohypertrophy, lipoatrophy and gynecomastia.

Although metabolic abnormalities such as hyperlipidemia or hyperglycemia are often associated with body changes, these events should be recorded separately at AE reporting.

#### 9.6. Pharmacokinetic Evaluations

#### 9.6.1. Evaluations

Pharmacokinetic assessments (sparse sampling) will be performed for all subjects randomized to the D/C/F/TAF arm to evaluate the pharmacokinetics of DRV. The pharmacokinetic samples may also be used for evaluation of the pharmacokinetics of COBI, FTC, TAF, and/or TFV, if deemed necessary, upon request of the study pharmacologist.

Single sparse blood samples will be collected on the Weeks 2 through 48 visits and the ESTD visit if applicable. Samples should be taken at least 15 minutes postdose if the regular dosing time coincides with the study visit or at any time during the visit if the dosing time does not coincide with the scheduled study visit.

All samples for pharmacokinetic analyses will be collected, identified and handled according to the laboratory manual. Exact dates and times of blood sampling, intake time of investigational medication, and whether this was taken with an accompanying meal, for the last 2 doses of investigational medication prior to the pharmacokinetic sampling must be recorded in the eCRF.

Pharmacokinetics of the ARVs in the control arm may also be evaluated (for which stored plasma samples may be used; see Section 9.1.1.1), if deemed necessary and upon request of the study pharmacologist.

### 9.6.2. Analytical Procedures

Plasma concentrations of DRV will be analyzed by the bioanalytical laboratory contracted by and under the supervision of the sponsor, using validated high-performance liquid chromatography-tandem mass spectroscopy (LC-MS/MS) methods. The bioanalyses will be performed in batches. Determination of the plasma concentrations of COBI, FTC, TAF, and/or TFV or ARVs in the control arm may be done upon sponsor's request, using validated methods, in a similar manner.

A description of the assays and validation data will be included in separate reports.

Results of bioanalyses will not be made available to the investigators.

#### 9.6.3. Pharmacokinetic Parameters

Based on the individual plasma concentration-time data, using the actual dose taken and the actual intake and sampling times, the following pharmacokinetic parameters may be derived using population pharmacokinetic modeling and Bayesian feedback, if appropriate population pharmacokinetic models are available.

- $C_{0h}$  and  $AUC_{24h}$  for DRV;
- $C_{0h}$  or  $C_{Xh}$  and  $AUC_{24h}$  for COBI, FTC, TAF, and/or TFV, or  $AUC_{12h}/AUC_{24h}$  as applicable for ARVs in the control arm, if deemed necessary, upon request of the study pharmacologist.

# 10. SUBJECT COMPLETION/WITHDRAWAL

#### 10.1. Completion

In the period up to Week 96, subjects will be considered to have completed study treatment if he or she has continued study medication intake up to Week 96 and has completed assessments at Week 96. Subjects who prematurely discontinue study treatment for any reason before completion of the 96-week treatment period will not be considered to have completed treatment.

In the period after Week 96, subjects will be considered to have completed study treatment if he or she continued study medication intake until D/C/F/TAF becomes commercially available and is reimbursed, or can be accessed through another source in the country where he/she is living, or until the sponsor terminates clinical development and has completed assessments until that point. Subjects who prematurely discontinue study treatment for any reason before that point, will not be considered to have completed the post Week 96 D/C/F/TAF treatment period.

#### 10.2. Withdrawal From the Study

A subject will be withdrawn from the study for any of the following reasons:

- Lost to follow-up.
- Withdrawal of consent.
- Subject request to stop study treatment for any reason.
- The investigator or sponsor believes (eg, for safety or tolerability reasons such as an AE, or for efficacy reasons) it is in the best interest of the subject to stop study treatment. The sponsor should be contacted for further discussion and final decision.
- Unacceptable toxicity, as defined in the toxicity management Section 9.5 of this protocol.
- Toxicity that, in the judgment of the investigator, compromises the ability to continue study-specific procedures.
- Pregnancy has been determined in participating female subjects.
- The subject develops clinical hepatitis.
- Discontinuation of the study at the request of the sponsor, DMC, the concerned regulatory agency or Independent Ethics Committee (IEC)/ Institutional Review Board (IRB).

A subject's study treatment may be discontinued if:

- An SAE occurs
- The subject fails to comply with the protocol or study staff requirements
- The subject starts disallowed treatment

- Intercurrent illness that would, in the judgment of the investigator, affect assessments of clinical status to a significant degree
- The subject demonstrates virologic rebound; see also Section 9.3.

If an investigator considers withdrawing a subject from study treatment for 1 of the above reasons, he /she should contact the sponsor for further discussion and final decision, unless the medical condition requires immediate action that cannot await contact with the sponsor.

Subjects who prematurely discontinue or change study treatment during the treatment phase (from Day 1 to Week 48) or during the extension phase (only between Week 48 and 96) will be required to complete the ESTD assessments within 72 hours of stopping/changing study treatment.

In addition, a 30-day follow-up (FU) visit will be required for any subject has an ongoing AE or SAE at the time of his/her last study visit (unless consent is withdrawn).

If a subject is lost to follow-up, every reasonable effort must be made by the study-site personnel to contact the subject and determine the reason for discontinuation/withdrawal. The measures taken to follow up must be documented.

When a subject withdraws before completing the study, the reason for withdrawal is to be documented in the eCRF and the source document, at the final evaluation the Trial Termination section of the eCRF must be completed. Study drug assigned to the withdrawn subject may not be assigned to another subject. Subjects who withdraw will not be replaced.

Subjects who withdraw consent from the bone investigation substudy (see Section 16.2.3) can still continue to participate in the main study.

#### Withdrawal From the Use of Samples in Future Research

The subject may withdraw consent for use of samples for research (refer to Section 16.2.5, Long-Term Retention of Samples for Additional Future Research). In such a case, samples will be destroyed after they are no longer needed for the clinical study. Details of the sample retention for research are presented in the main ICF.

#### 11. STATISTICAL METHODS

Statistical analysis will be done by the sponsor or under the authority of the sponsor. A general description of the statistical methods to be used to analyze the efficacy and safety data is outlined below. Specific details will be provided in the Statistical Analysis Plan.

The following analyses will be performed:

• A formal DMC analysis for monitoring purposes including a futility analysis for lack of (non-inferior) efficacy and a blinded sample size re-estimation (see also Section 11.9).

- The planned Week 24 interim analysis: once all subjects have completed the Week 24 assessments or discontinued earlier. This analysis will be done mainly to evaluate the safety and tolerability of D/C/F/TAF. However, efficacy of the 2 treatment arms will also be looked at. Results of which will also be shared with the DMC.
- The primary analysis: once all subjects from the D/C/F/TAF arm have completed the Week 48 assessments or all subjects from the control arm have completed the Week 52 assessments (whichever comes last), or discontinued earlier.
- The Week 96 analysis: once all subjects have completed the Week 96 assessments or discontinued earlier.
- The final analysis: once all subjects have completed the extension phase assessments and the 30-day FU visit (if applicable), or discontinued earlier.
- Additional statistical analyses may be done as needed to prepare for interactions with regulatory authorities.

# 11.1. Analysis Objectives and Endpoints

An overview of the objectives and hypothesis tested in this analysis is provided in Section 2. The analysis endpoints are listed below.

# 11.1.1. Primary Endpoint

The primary endpoint is the proportion of subjects having confirmed virologic rebound (confirmed HIV-1 RNA  $\geq$ 50 copies/mL through 48 weeks of treatment up to and including the upper bound of the Week 48 window, or in case of early discontinuation a last single viral load of HIV-1 RNA  $\geq$ 50 copies/mL).

# 11.1.2. Secondary Endpoints

Secondary endpoints in this study are:

- The proportion of subjects having confirmed virologic rebound through 24 and 96 weeks of treatment;
- The time to virologic rebound in weeks;
- The proportion of subjects experiencing grade 3 and 4 AEs through 24, 48, and 96 weeks of treatment;
- The proportion of subjects experiencing SAEs and premature discontinuations due to AEs through 24, 48, and 96 weeks of treatment;
- The change from baseline in serum creatinine, eGFRcr (by Cockcroft-Gault and by CKD-EPI) and eGFRcyst (by CKD-EPI) at Weeks 24, 48, and 96;
- The change from baseline in renal biomarkers at Weeks 24, 48, and 96;

- Clinical Protocol TMC114IFD3013 Amendment 4
- The proportion of subjects with HIV-1 RNA <20, <50, and <200 copies/mL at Weeks 24, 48, and 96 as defined by the FDA snapshot analysis and TLOVR algorithm;
- The change from baseline in CD4+ cell count at Weeks 24, 48, and 96;
- Adherence to drug intake based on drug accountability through 24, 48, and 96 weeks;
- Genotypic, and phenotypic if applicable, resistance to ARVs in the 2 treatment arms in subjects with confirmed HIV-1 RNA rebound through Weeks 24, 48, and 96;
- Pharmacokinetic parameters for DRV in the D/C/F/TAF arm.

Secondary endpoints to be assessed in subjects participating in a bone investigation substudy at selected study sites:

- The percent change from baseline in bone biomarkers CTX, P1NP, PTH, and 25-hydroxy vitamin D at Weeks 24, 48, and 96.
- The percent change from baseline in spine and hip BMD and change from baseline in BMD T-score at Weeks 24, 48, and 96.

#### 11.2. Sample Size Determination

A sample size of 1,100 subjects will yield 89% power if it is assumed that both treatment arms will have an equal rebound rate of 4% (confirmed HIV-1 RNA  $\geq$ 50 copies/mL up to, and including the upper bound of the Week 48 window or have discontinued prematurely, irrespective of reason, with the last available HIV-1 RNA  $\geq$ 50 copies/mL), that the noninferiority margin is 4%, and that the significance level of the test is at a 1-sided, 0.025 level.

Table 5 provides rebound rates from historical switch studies in virologically suppressed subjects and from the treatment-naïve study TMC114-C211 (ARTEMIS) in a subset of subjects (n=286) being virologically suppressed for at least 6 months (data available on file).

D/C/F/TAF (darunavir/cobicistat/emtricitabine/tenofovir alafenamide)

# NCT02269917

Clinical Protocol TMC114IFD3013 Amendment 4

Virologically Suppressed Patients			
Study	Treatment Arm	Rebound Rate (Snapshot a or Confirmed HIV-1 RNA ≥50 copies/mL)	Studied Patient Population
STRATEGY-PI (E/C/F/TDF switch f/bPI) 	bPI + FTC/TDF (N=139)	1.4% (Snapshot Week 48)	bPI + FTC/TDF; 6 months suppressed; 1 st or 2 nd ART; no history of VF and no RAMs to FTC/TDF in historical genotype
SPIRIT (RPV/FTC/TDF switch f/bPI) 	bPI + 2 NRTIs (N=159)	5% (Snapshot Week 24)	bPI + NRTIs; 6 months suppressed; 1 st or 2 nd ART; no history of VF and no RAMs to any study drug in historical genotype
SPIRAL (raltegravir switch f/bPI) 	bPI + 2 NRTIs (N=140)	4.3% (Confirmed HIV-1 RNA ≥50 copies/mL through 48 weeks)	6 months suppressed; VF on previous ART eligible
ARTEMIS b	DRV/rtv + FTC/TDF (N=286)	3.8% (Confirmed HIV-1 RNA ≥50 copies/mL through 48 weeks)	DRV/rtv + FTC/TDF; subset of patients at least 6 months suppressed

#### Rebound Rates (Snapshota or Confirmed ≥50 Copies/mL) From Historical Studies of Table 5:

ART=antiretroviral therapy; VF=virologic failure; f/bPI=from boosted PI

a HIV-1 RNA ≥50 copies/mL through 48 weeks or discontinuation due to lack of efficacy or discontinuations due t other reasons and last HIV-1 RNA  $\geq$ 50 copies/mL.

b Efficacy analysis performed after at least 6 months HIV-1 RNA <50 copies/mL.

For the bone investigation substudy, with 300 subjects (200 in the D/C/F/TAF treatment arm versus 100 in the control arm) and assuming an inter-subject variability of 4%, there is approximately 98% power to detect a 2% difference between the D/C/F/TAF treatment arm and the control arm in percent change from baseline in BMD at the spine. Other power calculations are presented in Table 6.

Table 6:	BMD at the L	umbar S	Spine, Pow	er Calcu	lations
		3.6		0	G

DMD 44b I and Got D

	Mean % Change from Baseline	Common Standard Deviation (%)	Power
	2	3.5	>99%
N=300	2	4	98%
IN-300	2	3.5	>99%
	5	4	>99%

#### 11.3. **Analysis Sets**

The intent-to-treat (ITT) population will include all the subjects who were randomized and received at least 1 dose of treatment subsequent to randomization in the study. Subjects will be grouped according to the treatment arm (D/C/F/TAF or control) to which they were randomized. The ITT analysis set is the primary analysis set for efficacy analysis. Efficacy data up to the last dose date of the randomized study treatment will be included. The safety analysis (including all data collected up to the 30-day FU visit) is also performed on this analysis set.

Since an analysis on the ITT population may not be conservative in a noninferiority setting, an analysis based on the per protocol (PP) population will also be performed to investigate the impact of excluding subjects with major protocol violations and to evaluate the robustness of the primary analysis results. The PP population will include all subjects who (1) are randomized into the study, (2) have received  $\geq 1$  dose of treatment in the study, (3) without any major protocol deviation that is considered to potentially affect efficacy outcomes (eg, previous DRV failure, use of concomitant medication interfering with antiviral efficacy, inadequate adherence to drug intake), and (4) have a baseline HIV-1 RNA value <50 copies/mL. Specific details will be provided in the Statistical Analysis Plan. The PP analysis set is the secondary analysis set for efficacy analysis.

The pharmacokinetic analysis set will include all subjects who are randomized to the D/C/F/TAF arm (and the control arm, if applicable) and have received at least 1 dose of investigational treatment (or control treatment, if applicable) in the study, and for whom plasma concentration data are available.

#### 11.4. Subject Information

For all subjects who sign an ICF and are randomly assigned to a treatment arm and receive at least 1 dose of study drug, descriptive statistics will be provided. Demographic and baseline disease characteristics will be summarized using standard descriptive methods (eg, sample size [n], mean, SD, median, minimum, maximum, frequency) as appropriate.

# 11.5. Efficacy Analyses

#### **Antiviral Efficacy**

The primary analysis will consist of a noninferiority evaluation of switching to the D/C/F/TAF single-tablet regimen (investigational treatment arm) versus maintaining the current regimen consisting of a bPI combined with FTC/TDF (control arm), with respect to the proportion of virologic rebounders through Week 48 after the start of treatment in this study. The rebounders are defined as

- subjects who show confirmed HIV-1 RNA ≥50 copies/mL up to, and including the upper bound of the Week 48 window (ie, 54 weeks),
- subjects who discontinued prematurely (irrespective of reason) for which the last available (single) HIV-1 RNA ≥50 copies/mL.

It will be concluded that the D/C/F/TAF single-tablet regimen is noninferior to the control regimen if the upper bound of the 2-sided 95% confidence interval (CI) of the difference between treatment arms (D/C/F/TAF arm - control arm) in rebounder rate is less than 4% (ie, a margin of 4% is applied to noninferiority assessment). The 2-sided 95% CI will be constructed using the stratum-adjusted Mantel-Haenszel difference in proportions, where the stratification factor (bPI used at screening) determines the strata.

If noninferiority of the D/C/F/TAF arm to control arm is established, the upper bound of the 95% CI will be compared to 0; if the upper bound of the 95% CI is less than 0, then superiority of D/C/F/TAF over the control arm will be established.

The proportion of subjects having confirmed virologic rebound through 24 and 96 weeks of treatment. Treatment difference (with 95% CI) through 24 and 96 weeks will be derived similary as for the primary efficacy parameter.

The proportion of subjects with HIV-1 RNA <20, <50, <200 copies/mL at Weeks 24, 48, and 96, as defined by the FDA snapshot analysis will be analyzed.

In addition, confirmed virologic response defined as HIV-1 RNA <20, <50, and <200 copies/mL at Weeks 24, 48, and 96 determined by the TLOVR algorithm will be analyzed.

The treatment arms will be compared by 95% CIs constructed using the stratum adjusted Mantel-Haenszel difference in proportions at Weeks 24 and 48, where the stratification factor (bPI at screening) determines the strata.

Time to virologic rebound will be graphically presented by means of Kaplan-Meier curves and the treatment groups will be compared by means of the Cox proportional hazards model including terms for treatments and bPI at screening.

#### Immunologic Change

The changes from baseline in CD4+ cell count at Weeks 24, 48, and 96 will be summarized using descriptive statistics. The difference in changes from baseline in CD4+ cell count between the 2 treatment arms and the associated 95% CIs at Weeks 24 and 48 will be constructed using ANCOVA, including term for bPI used at screening in the model and baseline CD4+ value as a covariate.

#### Resistance

HIV-1 genotypes, and phenotypes if applicable, will be analyzed from samples of subjects with confirmed virologic rebound (2 consecutive HIV-1 RNA values  $\geq$ 50 copies/mL or last available HIV-1 RNA  $\geq$ 50 copies/mL) and with HIV-1 RNA value  $\geq$ 400 copies/mL. The number of PR mutations (including International AIDS Society [IAS]-USA PI RAMs and IAS-USA primary PI mutations), and RT mutations (including IAS-USA NRTI RAMs and IAS-USA NNRTI RAMs), as well as specific mutations associated with resistance to DRV, FTC, TFV, and the PIs in the control treatment regimen (DRV, ATV, LPV) will be tabulated. Fold change (FC) in 50% effective concentration (EC50) of ARVs may be analyzed and tabulated.

### 11.6. Safety Analyses

#### Adverse Events

The original terms used by investigators to identify AEs will be coded using the Medical Dictionary for Regulatory Activities (MedDRA). All reported AEs with onset during the study will be included in the analysis. For each AE, the percentage of subjects who experience at least 1 occurrence of the given event will be summarized.

Summaries (number and percentage of subjects) of treatment-emergent AEs (by system organ class and preferred term) will be provided by treatment arm. Additional summaries will include summaries for AEs by severity grade (with special attention to grade 3 or 4 AEs), investigator's assessment of relationship to treatment, SAEs, and AEs leading to discontinuation of study treatment.

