# 9.4.1. Adverse Events/HIV-related Events

At each visit, from signing of the ICF, subjects will be asked about any untoward medical occurrences, and these will be recorded as AEs in the AE section of the eCRF. For detailed definitions and reporting procedures of AEs, please see Section 12.

Special attention will be paid to those subjects who discontinue the study for an AE, or who experience a severe AE (at least grade 3), or an SAE. For reported HIV events, further details will be recorded if these events are AIDS-defining illnesses (see World Health Organization [WHO] Clinical Staging of HIV/AIDS, Attachment 3). For subjects experiencing specific AEs, toxicity management should be done as described in Section 9.5.

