#### **General Instructions**

#### Estimating Severity Grade

If the need arises to grade a clinical AE that is not identified in the DAIDS grading table, use the category 'Estimating Severity Grade' located at the top of the table on the following page. In addition, all deaths related to an AE are to be classified as grade 5.

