5.4.2. Analysis Methods

A summary will be provided for the following treatment-emergent adverse events:

- any adverse events,
- serious adverse events,
- deaths due to AE,
- adverse events by toxicity grade (as well as AEs with toxicity grade at least 2 and AEs with toxicity grades 3 or 4),
- AEs at least possibly related to study medication,
- AEs for which the medication was temporarily/permanently stopped,
- serious adverse events that were at least possibly related to the medication.

Incidences of AEs for above mentioned analyses will also be presented by SOC and preferred term. There will be no formal statistical testing.

Summary of events and incidence tabulations for individual adverse events will be provided for AEOI and also for ADRs.

AIDS defining illness based on WHO clinical staging will be tabulated.

The number and percentage of subjects who experienced fracture events (subgroups Fracture, possibly osteoporotic and Fracture other of the Bone AEOI for fractures) will be summarized by treatment group.

Selected safety endpoints will be explored by subgroups defined in section 2.7.2. Details for subgroup analyses of safety endpoints will be provided in the DPS.

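### The secondary endpoint of grade 3 and 4 AEs, and one matching SAP table line, leave out grade 5, the grade the protocol assigns to every AE-related death

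*Protocol*

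**What the plan says.** **Grading rule.** Protocol Section 12.1.3 makes the DAIDS table in Attachment 2 the severity scale, and SAP 5.4.1 carries it over. The general instructions in Attachment 2 (Estimating Severity Grade) state that "all deaths related to an AE are to be classified as grade 5".

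**Endpoint.** Protocol 11.1.2, repeated in the synopsis, lists as a secondary endpoint "The proportion of subjects experiencing grade 3 and 4 AEs through 24, 48, and 96 weeks of treatment".

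**Week 96 tables.** SAP 5.4.2 lists "adverse events by toxicity grade (as well as AEs with toxicity grade at least 2 and AEs with toxicity grades 3 or 4". The same list contains serious AEs and deaths due to AEs, and the section adds that incidences for the listed analyses are also shown by system organ class and preferred term.

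**Protocol tables.** Section 11.6 states: "All reported AEs with onset during the study will be included in the analysis". It plans "summaries for AEs by severity grade (with special attention to grade 3 or 4 AEs", that is, summaries across severity grades, with grades 3 and 4 only singled out for attention.

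**Another cut-off.** Section 9.4.1, on AE recording, asks for special attention to subjects who "experience a severe AE (at least grade 3", which has no upper limit.

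**The concern.** The grading scale used here has five values, and the endpoint selects two of them. A programmer who follows the text will filter on grade 3 or 4, and an AE that ended in death will not pass the filter. The SAP shows the mismatch within one sentence: it asks for "AEs with toxicity grade at least 2 and AEs with toxicity grades 3 or 4". The first category is open at the top and takes in grade 5. The second is closed and does not. A subject with only a fatal AE therefore appears in the broader table and is missing from the narrower one, which reads like a drafting slip rather than a decision.

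What is at stake is the meaning of one safety proportion. A reader will take it as the share of subjects with a severe event or worse, as Section 9.4.1 would suggest. As worded, it is the share with a severe or life-threatening event that was not fatal. Any error is in the reassuring direction.

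**Working it through.** The plan states no figure to reproduce, so the check compares the rules and then sizes one missed subject.

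**Step 1: apply the rules to three kinds of subject.**

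| Subject's AEs | Endpoint in 11.1.2 and SAP line for grades 3 or 4 | SAP tables by grade, and grade 2 and above | SAP serious AEs | SAP deaths due to AE |
|---|---|---|---|---|
| One grade 4 AE, survived | counted | counted | counted if it meets a seriousness criterion | no |
| One fatal AE (grade 5), no other grade 3 or 4 AE | **not counted** | counted | counted | counted |
| One fatal AE plus a separate grade 3 or 4 AE | counted | counted | counted | counted |

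Only the second row goes wrong, and only in the first results column. Fatal AEs reach the serious-AE column because Section 12.1.1 makes a fatal outcome a seriousness criterion.

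**Step 2: look for text that restores grade 5.** None was found in the endpoint lists, Section 11.6, Section 12.1.3 or SAP 5.4. No text says either that grade 5 is deliberately reported only under deaths and serious AEs.

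**Step 3: size per missed subject.** The inputs are the planned arm sizes in Protocol 3.1: 734 for D/C/F/TAF and 367 for control.

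- D/C/F/TAF: 1/734 = 0.00136, or 0.14 percentage points.
- Control: 1/367 = 0.00272, or 0.27 percentage points.

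**Step 4: illustrative range.** The documents give no fatal-AE rate. As an assumption only, let 0% to 1% of subjects be of the second kind. The endpoint then misses 0 to 0.01 × 734 = 7.3 subjects (about 7) for D/C/F/TAF and 0 to 0.01 × 367 = 3.7 subjects (about 4) for control. The undercount is at most 1 percentage point in either arm.

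**Step 5: effect on the contrast.** If k₁ and k₂ subjects are missed in the D/C/F/TAF and control arms, the difference in proportions is off by k₁/734 − k₂/367. Equal rates cancel: with k₁ = 2 and k₂ = 1, 2/734 − 1/367 = 0. Only an imbalance in such deaths distorts the comparison. Under the range in Step 4 the distortion cannot exceed 1 point in either direction.

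**The case against.** The strongest reply is that no death goes unreported. Fatal AEs appear in the tables by grade, in those for grade 2 and above, among serious AEs and under deaths due to AEs, each also by system organ class and preferred term. They also count towards the serious-AE secondary endpoint, which stands next to this one at the same time points. An arm with more deaths would show that plainly. The endpoint also names its grades and does not call itself a severe-AE endpoint, and Section 9.4.1 concerns which subjects to watch, not how to analyse them. AE comparisons are not formally tested (SAP 5.4.2), and the SAP supplied covers only Week 96, so the table specifications for the randomised comparisons at Weeks 24 and 48 cannot be seen.

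Most of this stands, and it rules out three stronger inferences that a reader might draw:

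- *That the severity tables as a whole drop deaths.* Section 11.6 sets no such restriction, and SAP 5.4.2 plans open-ended tables.
- *That a death lowers the proportion.* It only fails to add a subject, and a subject with another grade 3 or 4 AE is still counted.
- *That an arm with more deaths is made to look safer overall.* The neighbouring serious-AE endpoint and the deaths line move the other way.

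The reply does not remove the narrow point. The other outputs are separate results and do not correct the proportion reported under this endpoint. The wording of Section 9.4.1 is not an endpoint definition, but it does show that the protocol elsewhere treats the top of the scale as open.

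**Conclusion.** The point holds in a limited form. The grade 3 and 4 endpoint (synopsis and Section 11.1.2) and the SAP 5.4.2 line for the same grades do not count a subject whose only severe AE was fatal. Safety reporting otherwise captures fatal AEs. The effect is 0.14 points per missed subject for D/C/F/TAF and 0.27 points for control, and probably small in total.

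This rests on three assumptions:

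- The database carries grade 5 for fatal AEs, as Attachment 2 instructs.
- The filter is programmed as literally written.
- The planned arm sizes apply. They do not carry over directly to the extension-phase tables for late switchers, whose number the SAP does not state.

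The documents do not support any claim about actual between-arm distortion, because neither the fatal-AE rate nor the Week 24 and Week 48 table specifications are available.

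**What to change.** - In the synopsis endpoint list and Section 11.1.2, define the endpoint as the proportion of subjects with an AE of grade 3 or higher (grades 3, 4 or 5).
- Make the same change to the SAP 5.4.2 line and its tables by system organ class and preferred term.
- Align the special-attention wording in the synopsis safety analyses and Section 11.6. The tables planned there need no structural change.
- If the narrower endpoint is intended, say instead that grade 5 is excluded on purpose and reported only under deaths and serious AEs.
- Because the SAP describes the Week 24 and Week 48 analyses as already done, state in the Week 96 report which rule those analyses used, so that the three time points can be compared.

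The cost is a wording change and one condition in the table program. No new data are needed.
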